8.4.2 Electrocardiogram (ECG)

Figure 8-1 Timing of study procedures

Full details of all procedures relating to the ECG collection and reporting are contained in the technical manual provided by the core laboratory.

ECGs must be recorded after the participant rests for 10 minutes, in supine position, to ensure a stable baseline and heart rate. Thereafter, three ECG should be taken at approximately 1 or 2-minutes intervals (i.e., in triplicate) with ECG machines supplied by the core laboratory. The

preferred sequence of cardiovascular data collection during study visits is ECG collection first, followed by vital signs. The Fredericia QT correction formula (QTcF) must be used for clinical decisions. The investigator must calculate QTcF if it is not auto-calculated by the ECG machine. The mean QTcF value for each visit will be calculated from the triplicate ECGs for each participant.

Triplicate 12 lead ECGs are to be collected with ECG machines supplied centrally. The ECGs must be reviewed by qualified site personnel in the first instance (e.g., cardiologist at site) and transmitted to the vendor as soon as possible after finishing the examination, for central review. The results of the centrally assessed ECGs will be electronically transferred into the clinical database.

Any original ECG not transmitted to the vendor electronically should still be forwarded for central review. A copy of the ECG tracing should be labeled with the study number, participant initials (where regulations permit), participant number, date, and kept in the source documents at the study site.

Clinically significant ECG abnormalities present prior to randomization should be reported on the Medical History CRF page. New or worsened clinically significant findings occurring after randomization must be recorded on the Adverse Events CRF page.

A monitoring or review process should be followed for clinically significant ECG findings throughout the study and especially at baseline before administration of study treatment (see also Section 10.2.3 for details).

8.4.2.1 Cardiac imaging - MRA (magnetic resonance angiography), MUGA (multiple gated acquisition) scan or echocardiogram

Not applicable

8.4.2.2 Cardiac enzymes

Not applicable

8.4.3 Pregnancy and assessments of fertility

Contraception

During the study, investigators should ensure that study participants are regularly reminded of the importance of complying with the highly effective method of contraception, as it is applicable to them.

Women of child-bearing potential (WOCBP), must use highly effective methods of contraception during dosing and for 1 week after stopping of investigational drug. For WOCBP, highly effective contraception methods include:

• Total abstinence from heterosexual intercourse (when this is in line with the preferred and usual lifestyle of the subject). Periodic abstinence (e.g. calendar, ovulation, symptothermal, post-ovulation methods) and withdrawal are not acceptable methods of contraception.

- Female sterilization (have had surgical bilateral oophorectomy with or without hysterectomy), total hysterectomy or tubal ligation at least six weeks before taking investigational drug. In case of oophorectomy alone, only when the reproductive status of the woman has been confirmed by follow up hormone level assessment.
- Male sterilization (at least 6 months prior to screening). For female participants on the study the vasectomized male partner should be the sole partner for that participant.
- Use of an intrauterine device (IUD) or intrauterine system (IUS). In case of use of an IUD or IUS, the device or system should have been placed and well tolerated by the patient for a minimum of 3 months before taking the study treatment
 Use of oral (estrogen and progesterone), injected or implanted hormonal methods of contraception other forms of hormonal contraception are not allowed for the purpose of contraception.

If local regulations deviate from the contraception methods listed above and require more extensive measures to prevent pregnancy, local regulations apply and will be described in the ICF.

A condom is required for all sexually active male participants to prevent them from fathering a child AND to prevent delivery of study treatment via seminal fluid to their partner while taking investigational drug and for 1 week after stopping study treatment. In addition, male participants should not donate sperm for the time period specified above.

Pregnancy testing

All pre-menopausal women who are not surgically sterile will have pregnancy testing. See the Assessment schedule (Table 8-1), for timing of the protocol required pregnancy testing; additional pregnancy testing may be performed to meet local requirements. In case of a positive urine pregnancy test at Baseline, study treatment must not be administered.

Serum pregnancy testing will be conducted, unless specified otherwise.

Refer to Section 10.1.4 for details on Reporting Pregnancy.

Assessments of fertility

Medical documentation of oophorectomy, hysterectomy, or tubal ligation must be retained as source documents. Subsequent hormone level assessment to confirm the woman is not of child-bearing potential must also be available as source documentation in the following cases:

- 1. Surgical bilateral oophorectomy without a hysterectomy
- 2. Reported 12 months of natural (spontaneous) amenorrhea with an appropriate clinical profile.

In the absence of the above medical documentation, luteinizing hormone (LH) and follicle stimulating hormone (FSH) testing is required of any female participant regardless of reported reproductive/menopausal status at screening.

8.4.4 Safety evaluations related to mechanism of action of MIJ821

To further assess safety events associated with the mode of action of MIJ821 in participants, the following assessments are to be conducted:

- CADSS
- MOAA/S
- Memory assessment using orientation questions

8.4.4.1 Clinician-Administered Dissociative States Scale (CADSS)

The CADSS is a questionnaire that assesses dissociative effects. Each item is scored from 0 to 4 and individual scores are summed to obtain a total score ranging from a minimum of 0 to a maximum of 92. The trained staff administering the scale will also note their subjective interpretation of the participant's mental status and overall wellbeing, and whether any findings could be related to study drug. In this study, the following recall periods will be used: "current".

The CADSS will be administered electronically by qualified site personnel according to Table 8-1.

8.4.4.2 Modified Observer's Assessment of Alertness/Sedation (MOAA/S)

The purpose of this scale is to assess participant responsiveness on a scale from 0 (= Does not respond to painful trapezius squeeze) to 5 (= Responds readily to name spoken in normal tone [awake]).

The MOAA/S will be administered electronically by qualified site personnel according to Table 8-1.

8.4.4.3 Memory Assessment using orientation questions

Memory gaps/amnesia are AEs of Special Interest (AESI). Memory Assessment using orientation questions will be assessed by qualified personnel according to Table 8-1.

Orientation questions will be asked to assess presence or absence of amnesia, as well as any distress for the participant, at defined intervals. The outcome of this assessment will only be captured in the eCRF if amnesia is assessed as an AE. In that case, the onset and resolution of amnesia should be identified as precisely as possible and these data will be recorded in the eCRF. While definite amnesia must be reported as an AE in the eCRF, possible mild amnesia may or may not be reported as an AE based on investigator judgment.

8.4.5 Oxygen saturation

Pulse oximetry will be used to measure arterial oxygen saturation during the 4-hour observation period on the dosing day. The device will be attached to the finger, toe, or ear before study drug administration. Then, oxygen saturation will be monitored and documented in the source documents at site. Any arterial oxygen saturation (SpO2) <93% should be confirmed by an additional measurement on another part of the body. On the day of study drug administration, pulse oximetry will be recorded every 15 minutes starting from pre-dose until 4 hours post-dose. If oxygen saturation levels are <93% at any time during the 4 hour postdose interval, pulse

oximetry will be recorded every 5 minutes until levels return to \geq 93% or until the participant is referred for appropriate medical care, if clinically indicated.

8.4.6 Appropriateness of safety measurements

The safety assessments selected are standard for the study population and compounds with similar mechanism of action. As explained in Section 4.1.3, the safety assessments and their frequency were selected based on the completed FIH and PoC studies and the ongoing SAD study with s.c. MIJ821 in HVs.

8.5 Additional assessments

8.5.1 Clinical Outcome Assessments (COAs)

As per Section 4.6, during a Public Health emergency as declared by Local or Regional authorities i.e. pandemic, epidemic or natural disaster, that limits or prevents on-site study visits, COA data may be collected remotely.

8.5.1.1 Clinician Reported Outcomes (ClinRO)

ClinROs will be used to establish the diagnosis of depression and to assess and record the patient's treatment history at Screening. They will also be used to measure the impact of MIJ821 on suicidality and disease severity with the following tools:

- SCID-5
- MGH-ATRO
- C-SSRS

Structured Clinical Interview for DSM-5 (SCID-5)

The SCID-5 is a semi-structured interview guide for DSM-5 disorders. It is administered by qualified personnel who are familiar with the DSM-5 classification and diagnostic criteria. The version used for this trial is the SCID-5-Clinical Trials version (SCID-5-CT). It guides the clinician step-by-step, through the DSM-5 diagnostic process, and allows to assess whether the diagnostic criteria have been met. Interview questions are provided along each corresponding DSM-5 criterion, which aids in rating each criterion as either present or absent. The SCID-5-CT covers the DSM-5 diagnoses most commonly seen in clinical settings.

The SCID-5-CT will be administered at screening only, as indicated in the Assessment Schedule Table 8-1. The SCID-5-CT responses will be recorded as source documentation only and will not be entered in the database.

[figure not shown]
Massachusetts General Hospital Antidepressant Treatment Response Questionnaire (MGH-ATRQ)

The MGH-ATRQ examines the adequacy of duration and dose of prior and current antidepressant treatments in a step-by-step procedure (Chandler 2010). When assessing the duration and dose of antidepressants, the examiner must always inquire about adherence to each treatment. In addition, the MGH-ATRQ assesses the degree of improvement on a scale from 0% (not improved at all) to 100% (completely improved).

The MGH-ATRQ will be administered at screening. Treatments with a response of "less than 25% improved" will be considered failed treatments. All treatments (failed and successful) used in the current episode for each participant should be listed on the MGH-ATRQ and entered in the corresponding CRF page. All treatments listed on the MGH-ATRQ and on-going at the time of screening should also be entered in the Concomitant Medication CRF page.

Columbia Suicide Severity Rating Scale (C-SSRS)

The C-SSRS is a questionnaire that prospectively assesses suicidal ideation and suicidal behavior. The C-SSRS will be administered as defined in Section 8. In this study, the following recall periods will be used: "one month/one year" and "since last evaluation". Further details on the C-SSRS procedure are given in Section 10.2.4.

8.5.2 Pharmacokinetics

Pharmacokinetic (PK) samples will be collected at the time points defined in the assessment schedule (Table 8-1). Follow instructions outlined in the central laboratory manual regarding sample collection, numbering, processing and shipment.

In order to better define the PK profile, the timing of the PK sample collection may be altered based on emergent data. The number of samples/blood draws and total blood volume collected will not exceed those stated in the protocol.

In case of unscheduled visits for safety monitoring purposes during the time period from 4 h to 24 h after injection, unscheduled PK samples may be collected if operationally feasible.

PK samples will be collected in all participants to avoid unblinding. Only samples from participants treated with MIJ821 will be analyzed.

Pharmacokinetic analytical method(s)

Concentration in plasma of MIJ821 will be determined by validated LC-MS/MS method. The lower limit of quantification (LLOQ) of MIJ821 in plasma is considered to be 0.1 ng/mL. Concentrations will be expressed in mass per volume units. Concentrations below the LLOQ will be reported as "zero" and missing data will be labeled as such in the Bioanalytical Data Report. Samples collected from placebo-treated participants will not be measured.

Pharmacokinetic parameters

The following PK parameters of MIJ821 will be determined using the actual recorded sampling times and non-compartmental method(s) with Phoenix WinNonlin (Version 8 or higher):

- primary PK parameters: AUClast, Tmax, and Cmax
- secondary PK parameters: if data permit, additional PK parameters will be estimated e.g. T1/2, Area Under the Curve from time zero to infinity (AUCinf), AUC0-t (if needed, time range to be defined during PK analysis), CL/F, Vz/F (data not limited)

The linear trapezoidal rule will be used for AUC calculation. Regression analysis of the terminal elimination phase for the potential determination of T1/2 will include at least 3 data points after Cmax. If the R² value of the regression analysis of the terminal phase will be less than 0.75, no values will be reported of PK parameters depending on the estimation of the terminal elimination phase (e.g. CL/F, Vz/F, AUCinf).

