2.2 Secondary estimands

Not applicable

3 Study design

Figure 3-1 Study Design

This is a non-confirmatory, randomized, double-blind, placebo-controlled, parallel-group trial in participants with TRD to evaluate the efficacy, safety, tolerability and pharmacokinetics of single subcutaneous MIJ821 administration in addition to pharmacological antidepressant SoC treatment. Approximately 56 participants will be randomized in a total of 20-25 centers worldwide.

Participants will be randomly allocated to one of the following four treatment arms in a 1:1:1:1 ratio:

- Single administration of MIJ821 s.c. 10 mg
- Single administration of MIJ821 s.c. 4 mg
- Single administration of MIJ821 s.c. 1 mg
- Single administration of Placebo s.c.

The screening period starts when the participant signs the informed consent form and can last up to 28 days. The eligibility of participants is determined based on the assessments performed during the screening period and also on Day 1, prior to randomization. With the exception of lab results, all other baseline evaluations including the primary efficacy scale (MADRS) must be performed on Day 1, prior to randomization, and reviewed against the eligibility criteria before dosing. On Day 1, eligible participants will then be randomized to one of the above treatment arms.

Treatment is administered as a single s.c. injection on Day 1, followed by a safety observation at the clinical site for a minimum of 4 hours after administration. Study participants will be continuously observed by site personnel during the first 30 minutes after administration for emergence of adverse events, particularly CNS or cardiovascular AEs. Safety assessments will

include physical examinations (PEs), ECGs, vital signs, standard clinical laboratory evaluations (hematology, blood chemistry, and urinalysis), administration of the CADSS, MOAA/S, C-SSRS, and memory assessment using orientation questions. Local tolerability will be evaluated by visual inspection of the injection area. Injection site abnormalities reaching the threshold of mild changes will also be assessed quantitatively (refer to Section 8.5.4).

Participants will be allowed to leave the clinical site at the earliest 4 hours after dosing, if all of the following criteria are fulfilled:

- The participant does neither report nor present with any CNS adverse events (dissociation, amnesia, sedation)

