Hematology	X ¹¹	Χ										Х								Χ
Clinical Chemistry	X ¹¹	Χ										Χ								Χ
Coagulation Panel	X ¹¹	X										Х								Х
Urinalysis	X ¹¹	Х										Χ								Х
PK blood collection ¹²			X8	Х	Х	Х	Х	х	Х	Х	X	X ⁹								

Pariod Carooning	Trootmo
Amended Clinical Trial Proto	ocol (Version No. 02, Clean)

Period	Screening					Trea	tment						Follow-up							
Visit Name	Screening									Follow- up call	Follow- up visit	Follow- up call	Follow- up visit	Follow- up call	Follow- up visit	Follow- up call				
Visit Numbers ¹	1		20 40							50	60	70	80	90	100	110	120			
Days	-28 to -1					1						2	4	8	11	15	18	22	25	29
Time (post-dose)	ı	- 1h	0h	0.17h	0.33h	0.5h	0.75h	1h	1.5h	2h	4h	24h	-	-	-	-	-	-	-	-
Randomization		Х																		
Dose administration			Х																	
MADRS	Х	Χ									Χ	Χ		Х		Х		Χ		Х
Concomitant therapies	Х	Х										Х	Х	Х	Х	Х	Х	Х	Х	Х
Adverse Events	Х	Χ	Х		Х		Х			Х	Χ	Χ	Х	Х	Х	Х	Х	Х	Х	Х
Study completion information																				Х
Safety follow-up call													Х		Х		Х		Х	

X Assessment to be recorded in the clinical database or received electronically from a vendor

1 Visit structure given for internal programming purpose only

2 Optional for participant

3 S = assessment to be recorded on source documentation only and will not be entered into the eCRF. If drug screen result is positive but does not meet DSM-5 criteria for substance use

- ⁴ Additional pregnancy testing may be performed at each visit to meet local requirements. Serum pregnancy test to be performed, unless specified otherwise.
- ⁵ Urine pregnancy test. Dosing can proceed only if result is negative.
- ⁶ Dosing can proceed if the results are deemed satisfactory by the Investigator.
- ⁷ Every 15 minutes from pre-dose to 4 hours post-dose
- ⁸ Pre-dose
- ⁹ Approximately 24 hours after the injection

disorder, the subject can be randomized.

- ¹¹ All screening laboratory results must be obtained before randomization to ensure participants eligibility
- ¹² In case of unscheduled visits for safety monitoring purposes during the time period from 4 hours to 24 hours after injection, unscheduled PK samples may be collected if operationally feasible.
- ¹³ The outcome of this assessment will only be captured in the eCRF if amnesia is considered as an AE

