12.5.3 Pharmacokinetics

MIJ821 plasma concentrations will be expressed in mass per volume. The plasma concentrations will be listed by treatment/dose, subject number, and visit/sampling time point. Descriptive summary statistics of plasma concentrations will be provided by treatment/dose and visit/sampling time point including the frequency (n, %) of concentrations below the LLOQ and reported as zero. Summary statistics of plasma concentrations will include arithmetic and geometric mean, SD, and CV and median, minimum, and maximum. Concentrations below

LLOQ will be treated as zero in summary statistics and for PK parameter calculations. A geometric mean will not be reported if the dataset includes zero values.

PK parameters will be calculated as described in Section 8.5.2 and will be listed by treatment/dose and subject number. Descriptive summary statistics of PK pharmacokinetic parameters will be provided by treatment/dose. Summary statistics of pharmacokinetic parameters will include arithmetic and geometric mean, SD, and CV and median, minimum, and maximum. An exception to this is Tmax where median, minimum, and maximum will be presented.

[figure not shown]
Table 12-2	Non-compartmental pharmacokinetic parameters

AUClast	The AUC from time zero to the last measurable concentration sampling time (tlast) (mass x time x volume-1)
AUCinf	The AUC from time zero to infinity (mass x time x volume-1)
AUC0-t	The AUC for the defined time period from 0 hour to time t.
Cmax	The maximum (peak) observed plasma, blood, serum, or other body fluid drug concentration after single dose administration (mass x volume-1)
Tmax	The time to reach maximum (peak) plasma, blood, serum, or other body fluid drug concentration after single dose administration (time)
Lambda_z	Smallest (slowest) disposition (hybrid) rate constant (time-1) may also be used for terminal elimination rate constant (time-1)
T1/2	The elimination half-life associated with the terminal slope (λz) of a semi logarithmic concentration-time curve (time). Use qualifier for other half-lives
CL/F	The total body clearance of bioavailable drug from the plasma (volume x time-1)
Vz/F	The apparent volume of distribution of bioavailable drug during terminal phase (associated with λz) (volume)

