### 2.8.2 Descriptive analyses

In addition to the commonly used statistics, additional statistics will be used for summarizing the PK endpoints. The N values are defined as the number of participants with valid measures in each dose arms in the PK analysis set. The %CV (coefficient of variation percent) values will be summarized using the arithmetic mean calculated as '100\*(standard deviation / mean)' and the geometric mean calculated as 'sqrt (exp (variance for log transformed data)-1)\*100'.

All MIJ821 plasma concentrations and PK parameters including their descriptive statistics will be presented with three significant figures. The exception will be %CV values, which will be reported to one decimal place and N values, which will be reported as whole integers.

Concentrations below LLOQ will be treated as zero in summary statistics and for PK parameter calculations.

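### The linear trapezoidal rule overstates AUClast across the unsampled 4 to 24 h interval when the 24 h sample is measurable; linear-up/log-down is better but does not cure truncation at 4 h

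*Protocol*

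**What the plan says.** Protocol section 8.5.2 fixes one rule for every AUC: "The linear trapezoidal rule will be used for AUC calculation". The readable PK text of the SAP (sections 2.8.1 and 2.8.2) names no other rule, and SAP section 4 lists no change to the protocol analyses.

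The PK row of Table 8-1 has a pre-dose sample and post-dose samples at 0.17, 0.33, 0.5, 0.75, 1, 1.5, 2, 4 and 24 h. The footnote describes the last as "Approximately 24 hours after the injection". Nothing is scheduled between 4 h and 24 h. A sample in that gap can arise only at an unscheduled safety visit, if feasible. Section 8.5.2 adds that "the timing of the PK sample collection may be altered based on emergent data", but also that "The number of samples/blood draws and total blood volume collected will not exceed those stated in the protocol". Section 3 says: "Participants will be allowed to leave the clinical site at the earliest 4 hours after dosing".

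Table 12-2 ends AUClast at the last measurable sample. On the assay, section 8.5.2 says: "The lower limit of quantification (LLOQ) of MIJ821 in plasma is considered to be 0.1 ng/mL". SAP section 2.8.2 says: "Concentrations below LLOQ will be treated as zero in summary statistics and for PK parameter calculations".

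AUClast is one of three primary PK parameters. With Cmax, it is a named example of the exposure metric to be set against MADRS change (Protocol 12.5.6, SAP 2.9).

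**The concern.** Drug concentration falls along a convex curve after the peak, so a straight line between two points on the decline lies above it. Over 20 h the excess can be large, and under the linear rule this single segment can make up most of AUClast.

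Whether the segment counts at all depends on the 24 h result. If it is measurable, AUClast runs to 24 h and is inflated. If it is below the limit, AUClast stops at 4 h and omits the later exposure. Two participants just either side of 0.1 ng/mL therefore get AUClast values that are not comparable, and the split falls unevenly across doses. An unscheduled sample in the gap also changes AUClast, but only for those who had a safety visit.

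At stake are the AUClast summaries by dose and the AUClast axis of the trendline and Sigmoid Emax plots, in a study meant to inform dose selection.

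**Working it through.** **Inputs.** Sampling times: Table 8-1. Limit of quantification: 0.1 ng/mL (Protocol 8.5.2). Simulated mean Cmax: 73, 18 and 4 ng/mL at 10, 4 and 1 mg (Protocol 4.2.1). Exposure after 12 mg s.c. in healthy volunteers: mean AUClast 257 h·ng/mL and mean Cmax 77.4 ng/mL (Protocol 6.2.1). Half-life and Tmax are not given. I assume one compartment with first-order absorption, half-life 1.5 to 12 h and Tmax 0.33 to 1.0 h. The plan states no AUC error, so there is no figure of its own to reproduce.

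**1. The 4 to 24 h segment.** The linear rule gives 10 × (C4 + C24). With mono-exponential decline the true area is (C4 − C24) / k, where k = ln 2 / half-life.

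- Half-life 6 h, Tmax 0.75 h, 10 mg: C4 = 51.29, C24 = 5.09. Linear: 10 × 56.38 = 563.8. True: 46.20 / 0.1155 = 400. Ratio 1.41.
- Half-life 2.5 h, same Tmax and dose: C4 = 32.01, C24 = 0.125. Linear: 321.4. True: 31.89 / 0.2773 = 115. Ratio 2.79.

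The log rule gives 20 × (C4 − C24) / ln(C4 / C24), which equals the true area here.

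**2. Whole AUClast when the 24 h sample is measurable, relative to true AUC0–24.**

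| Half-life | Linear | Linear-up/log-down |
|---|---|---|
| 2.5 h (10 mg) | about 1.6 | 0.99–1.00 |
| 6 h | 1.25 | 1.00 |
| 8 h | 1.16 | 1.00 |
| 12 h | 1.08 | 1.00 |

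For example, at 6 h and 10 mg: 808.3 / 645.0 = 1.25. With assumed two-phase declines the linear rule gives 1.22 to 1.60 and log-down 1.04 to 1.19, so log-down reduces the error without removing it.

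**3. When the 24 h sample is below the limit.** AUClast stops at 4 h and is 0.48 to 0.84 of the true value. Changing the rule moves this by at most 0.02.

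**4. Where the switch falls.** Ignoring absorption, C24 equals 0.1 ng/mL when half-life = 24 × ln 2 / ln(Cmax / 0.1). That is 2.5, 3.2 and 4.5 h at 10, 4 and 1 mg. With absorption it is about 2.4–2.5, 3.0–3.1 and 4.3–4.4 h. Between these values, the mean profile at 10 mg is inflated while that at 1 mg is truncated.

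**5. The documents' only anchor.** 257 / 77.4 = 3.32 h. Read as one compartment, half-life is at most 3.32 × 0.693 = 2.3 h, or 1.4 to 2.1 h with Tmax 0.33 to 1.0 h. Even at 2.3 h, C24 at 10 mg is about 0.05 ng/mL, so every mean profile is truncated. With an assumed 30% CV (Tmax 0.5 h, median half-life 1.92 h), about 20% of 10 mg, 5% of 4 mg and 0.4% of 1 mg participants still have a measurable 24 h sample.

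**6. An allowed subgroup.** Protocol 6.2.1 permits strong CYP2D6 inhibitors, with simulated effects of at most 1.3-fold on Cmax and 2-fold on AUC. Applying both to the anchor: 3.32 × 2 / 1.3 = 5.11 h, or a half-life of 2.8 to 3.3 h with the same Tmax range. At 10 mg, C24 is then 0.3 to 0.7 ng/mL and linear AUClast is about 1.5 to 1.6 of true. An uninhibited 10 mg participant is truncated, at 0.73 to 0.82 of true. The apparent inhibited-to-uninhibited ratio is about 4.0 under the linear rule and 2.5 to 2.7 under log-down, against a true 2.0.

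**7. Across doses and participants** (30% CV on half-life and Cmax, Tmax 0.5 h). The true 10:1 mg ratio is about 73 / 4 = 18.2.

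| Median half-life | Linear 10:1 mg ratio | Log-down 10:1 mg ratio |
|---|---|---|
| 2 h | 22.7 | 20.5 |
| 2.5 h | 29.3 | 23.8 |
| 3 h | 34.4 | 26.3 |
| 6 h | 21.7 | 20.5 |

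For median half-lives of 1.5 to 8 h, the log-scale correlation of AUClast with true AUC within 10 mg is 0.88–0.98 linear and 0.95–1.00 log-down. Pooled over doses it is 0.980–0.996 and 0.990–0.998.

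**8. Unscheduled sample.** At 10 mg and half-life 2.5 h, one extra 8 h sample moves linear AUClast from 1.62 to 1.17 of true. Log-down stays at 1.00.

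**The case against.** The strongest reply is that the inflation may not be the typical case. Step 5 puts every mean profile below the limit at 24 h, where the choice of rule hardly matters and the sparse schedule is the real constraint. Near that anchor the linear rule even looks better on arm means: at 10 mg the mean ratio to true is 0.94 linear and 0.82 log-down. Much of the excess in step 7 is truncation at 1 mg, since log-down still gives 20.5 to 26.3. The plan also prespecifies its rule, lists and plots every concentration, reports the frequency below the limit, allows sample times to move, and names AUClast only as an example metric beside Cmax. Pooled correlations are high under either rule.

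Much of this stands, and it is why the point is minor. Truncation may be the commoner problem, and log-down does not repair it. The better arm mean, however, is accidental: inflation in some participants offsets truncation in others. For individual values, which the exposure-response plots use, log-down is closer in the same setting (within-10 mg log correlation 0.955 against 0.880; log-scale root mean square error 0.25 against 0.31). Across the cases run its log-scale error was lower, or at most 0.02 higher. Step 6 shows that inflation can occur even under the anchor. The freedom to move samples does not require one in the gap. SAP text after section 2.8.2 is partly redacted, so whether a model-based exposure metric is already planned cannot be judged.

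**Conclusion.** The concern holds as a minor point. The direction of the error follows from the convex decline. Its size does not follow from the documents: with a measurable 24 h sample it is roughly 8% to 60% too high for half-lives from 12 h down to 2.5 h under one compartment, and 22% to 60% too high in the two-phase profiles tried. Log-down brings this to between 1% low and 19% high. These figures rest on the assumed kinetic model, half-life and Tmax. The anchor further assumes that the exploratory healthy-volunteer AUClast approximates its true AUC, although that study's sampling times and AUC rule are not given.

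The consequence is limited to AUClast, any AUCinf or CL/F derived from it, and the AUClast exposure-response displays. Ordering across doses is nearly intact. Cmax, Tmax, the primary MADRS analysis and power are not touched, and the trial is non-confirmatory.

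**What to change.** State in SAP section 2.8.1, and in Protocol section 8.5.2 if it is amended: *AUC will be calculated by the linear-up/log-down trapezoidal rule.* Record the departure in SAP section 4, before database lock. A useful optional addition is to mark, in the SAP 2.9 plots, the participants whose AUClast ends at 4 h, because the change of rule does not help them.

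The cost is one software setting and one sentence, with no extra blood or visits. Editing the protocol text itself needs a written amendment and its approvals (Protocol 14.1); recording the change in the SAP is the lighter route. Comparability with earlier MIJ821 studies falls if they used the linear rule, which a footnote can state.

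Moving one existing draw into the gap would help more: with 0.75 h moved to 8 h, the linear ratio is 0.77 to 1.17, against 0.50 to 1.62 as scheduled. But participants would have to stay or return after 4 h, so it is not proposed here.
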